**run;**

In order to descriptively present the HbA1c data, measurement results from baseline and each scheduled post-baseline visit will be presented for FAS set. Results will be listed for SAF set. Change from baseline for FAS subjects will also be summarized for all scheduled post-baseline visits.

To evaluate the proportion of subjects achieving a glycemic response, defined as HbA1c <7.0% at Week 52, following hypothesis will be tested:

$$H_0: \pi_T = \pi_C \text{ Versus } H_A: \pi_T \neq \pi_C$$

In this secondary analysis, the successful event is to achieve an HbA1c <7.0 at Week 52. In above hypothesis,  $\pi_T$  denotes the probability of success for subjects received Dapagliflozin (Treatment under investigation, T) and  $\pi_C$  denotes the probability of success for subjects received Glimpiride (Comparator, C). To obtain a complete data structure, missing data will be imputed using LOCF.

The secondary variable will be analysed using a Logistic Regression model with treatment group and baseline measurement as factor, as following:

$$\text{Logit}(E(P_{ij})) = \beta_0 + \beta_1 \text{Trt}_i + \beta_2 \text{Base}_{ij}$$

Where  $i=1, 2; j=1, 2, \dots, n_i$ .

$\text{Logit}(E(P_{ij}))$  denotes the logit (log-odds) of the expected probability of success at Week 52 for the  $j^{\text{th}}$  subject in treatment group  $i$ .

$\text{Trt}_i$  denotes the treatment effect of each group.

$\text{Base}_{ij}$  denotes the baseline numeric test result (in this case, baseline HbA1c level) of  $j^{\text{th}}$  subject in treatment group  $i$ .

Above model will be applied to analyse the secondary efficacy endpoint. The model will be used to derive an estimated odds ratio between two treatment groups (treatment versus comparator) together with a 95% confidence interval and corresponding Wald two-sided p-value.

Following SAS code can be used to obtain above statistics:

```
proc logistic data=Data descending;  
class AVALC(ref='N') TRTP (ref='Comparator')/param=glm;  
model AVALC (ref='N')= TRTP Base/link=logit;  
lsmeans TRTP/e diff=CONTROL('Comparator') cl oddsratio;  
run;
```

In order to descriptively present the HbA1c classes, measurement results (proportion of subjects having HbA1c <7.0) from baseline will be presented for FAS set. Results will be listed for SAF set.

To evaluate the change in FBS levels from baseline to 52 weeks (4, 12, 24, 36 and 52 weeks), which is defined as the FBS level measured at Week 52 (4, 12, 24, 36 and 52 weeks) subtract the subject's baseline value.

The statistical modelling and analysis will be performed in the same manner as secondary efficacy variable HbA1c level using a MMRM model.

In order to descriptively present the FBS levels, measurement results from baseline and each scheduled post-baseline visit will be presented for FAS set. Results will be listed for SAF set. Change from baseline for FAS subjects will also be summarized for all scheduled post-baseline visits.

To evaluate the changes in body weight, waist circumference, BMI from baseline to 52 weeks (4, 12, 24, 36 and 52), which is defined as the corresponding results measured at Week 52 (4, 12, 24, 36 and 52) subtract the subject's baseline value.

The statistical modelling and analysis will be performed in the same manner as secondary efficacy variable HbA1c level using a MMRM model.

Descriptive presentation of body weight, waist circumference and BMI will be prepared together with other vital signs in FAS set.

To evaluate the changes in SBP and DBP from baseline to 52 (4, 12, 24, 36 and 52 weeks), which is defined as the results measured at Week 52 (4, 12, 24, 36 and 52 weeks) subtract the subject's baseline value.

The statistical modelling and analysis will be performed in the same manner as secondary efficacy variable HbA1c level using a MMRM model.

Descriptive presentation of blood pressure will be prepared for FAS set, and together with other vital signs in SAF set. Results will be listed for SAF set.

To evaluate the changes in abdominal VAT and SAT area, VAT/SAT ratio using abdominal CT from baseline to 52 weeks, which is defined as the results measured at Week 52 subtract the subject's baseline value.

The statistical modelling and analysis will be performed in the same manner as the primary efficacy variable using an ANCOVA model.

In order to descriptively present the VAT and SAT levels, measurement results (VAT, SAT and VAT/SAT ratio) from baseline and Week 52 will be presented for FAS set. Results will be listed for SAF set. Change from baseline to Week 52 for FAS subjects will also be summarized.

To evaluate the changes in lean mass using Dual Energy X-ray Absorptiometry (DXA) from baseline to 52 weeks, which is defined as the results measured at Week 52 subtract the subject's baseline value.

The statistical modelling and analysis will be performed in the same manner as the primary efficacy variable using an ANCOVA model.

In order to descriptively present the lean mass from baseline and Week 52 will be presented for FAS set. Results will be listed for SAF set. Change from baseline to Week 52 for FAS subjects will also be summarized.

To evaluate the changes in high-sensitivity CRP (hsCRP) and adiponectin from baseline to 52 weeks, which is defined as the results measured at Week 52 subtract the subject's baseline value.

The statistical modelling and analysis will be performed in the same manner as the primary efficacy variable using an ANCOVA model.

In order to descriptively present the hsCRP and adiponectin levels, measurement results from baseline and Week 52 will be presented for FAS set. Results will be listed for SAF set. Change from baseline to Week 52 for FAS subjects will also be summarized.

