Drug accountability of investigational product and metformin will be conducted.

Investigational product and metformin will be dispensed.

In case of glimepiride group, glimepiride can be up titrated to 2 mg to maintain glycaemic control at the discretion of the investigator after evaluation of glycaemic control in subjects. Glimepiride can be also down titrated to mitigate recurrent hypoglycaemic events at the discretion of the investigator but 0mg is not allowed. If further hypoglycaemic events occur with meeting the discontinuation criteria after taking the 1mg glimepiride, subjects may be discontinued from investigational product.

All serious adverse events will be reported.

Adverse Events will be collected from subject actually taking the IP.

Subjects will discontinue the study if one major hypoglycaemic event or recurring minor hypoglycaemic events (any recurrent events of hypoglycaemia, as judged by the investigator, not meeting the definition of major hypoglycaemic event) occur.

Randomized subjects who discontinue the study prematurely should immediately stop taking investigational product and complete the procedures described for Visit 7.

4.4 End of Treatment: VISIT 7

Physical exam contains measurement of weight, waist circumflex, pulse and blood pressure. BMI calculation will be conducted.

12 lead ECG will be conducted.

Subjects will be followed for laboratory assessment of efficacy and safety according to study plan FBG, HbA1c, CBC, AST, ALT, total bilirubin, BUN, creatinine, electrolytes, total cholesterol, triglyceride, HDL-cholesterol, urinalysis, hsCRP, adiponectin. All laboratory assessment will be done in central laboratory.

Diet and life-style counselling will be given to the subject.

DXA and abdominal CT measurement will be conducted.

Concomitant medications will be checked.

Drug accountability of investigational product and metformin will be conducted.

Subject diary will be reviewed for hypoglycaemic events.

All serious adverse events and adverse events will be reported and followed up

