8.4 Outcome measures for analyses

Efficacy Variables

- Change from Baseline: Change from baseline will be calculated as absolute difference between the values measured at a specific time point after baseline minus baseline value. Baseline value is defined to be Visit 2 (randomization).
- Proportion of subjects achieving a glycemic response, defined as HbA1c < 7.0% at Week 52.

If no measurements is available at Week 52, the last post-baseline HbA1c prior to Week 52 will be used instead for analysis.

Safety Variables

The following safety data will be collected: CBC, electrolytes, lipid, urinalysis, vital signs (pulse), reported hypoglycemic events and adverse events.

Change from screening (Visit 1) to each post-treatment time point where scheduled assessments were made will be calculated for CBC, electrolytes, lipid, and vital signs (pulse).

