### **3.1.4 Missing Data**

LOCF will be used for imputation of missing values of glycaemic control status (HbA1c <7.0%).

Last observation will be carried forward as many times as needed. All available data, including unscheduled visits and rescue visits, will be taken into account when identifying the last observation to be carried forward.

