### 3.8.2 Primary Analysis of Secondary Endpoints

To evaluate the difference between two treatment groups regarding change in HbA1c levels from baseline to 52 weeks (12, 24, 36 and 52 weeks), the following hypothesis will be tested:

$$H_0: \mu_T = \mu_C \text{ Versus } H_A: \mu_T \neq \mu_C$$

Where  $\mu_T$  denotes the mean change in test results from Baseline to Week 52 of subjects received Dapagliflozin (Treatment under investigation, T) and  $\mu_C$  denotes the mean change in test results from Baseline to Week 52 (12, 24, 36 and 52 weeks) of subjects received Glimepiride (Comparator, C).

The secondary variable will be analysed using a Mixed effect Model Repeat Measurement (MMRM) model with treatment group, visit, visit\*treatment group and baseline measurement as factors, as following:

$$E(Y_{ijk}) = \beta_0 + \beta_1 Trt_i + \beta_2 V_j + \beta_3 Trt_i \times V_j + \beta_4 Base_{ik}$$

Where  $i=1, 2$ ;  $j=1,2,\dots,5$ ;  $k=1, 2,\dots, n_i$ .

$E(Y_{ijk})$  denotes the change in test result from baseline to the  $j^{\text{th}}$  visit post-baseline of the  $k^{\text{th}}$  subject in treatment group  $i$ .

$Trt_i$  denotes the treatment effect of each group.

$V_j$  denotes the  $j^{\text{th}}$  visit post-baseline.

$Trt_i \times V_j$  denotes the interaction term of treatment group and visit.

$Base_{ik}$  denotes the baseline test result of  $k^{\text{th}}$  subject in treatment group  $i$ .

The above model will be applied to analyse the secondary efficacy endpoints. All non-missing visit data will be used. The model will be used to derive a least squares estimate of the treatment difference with a 95% CI and corresponding Wald two-sided p-value. Missing data will not be imputed.

The following SAS code can be used to obtain the above statistics:

```
proc mixed data=DATA; where AVISITN in (X,X,X,X) and  
PARAMCD="XXX";  
class TRTP AVISIT USUBJID;  
model AVAL=TRTP | AVISIT Base/solution;  
repeated AVISIT/type=un subject=usubjid r rcorr;  
lsmeans TRTP*AVISIT/diff=CONTROL('Comparator' 'Week52') cl;
```

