### **3.8.3 Sensitivity Analysis of Secondary Endpoints**

To assess the robustness of the missing data imputation (LOCF), the same model and statistics will be generated for FAS population with only truly observed data when evaluating proportion of subjects achieving a glycemic response.

To evaluate the impact of protocol compliance on secondary efficacy endpoint, secondary efficacy models (with imputed data for glycemic response) method will be repeated on the PPS population.

To evaluate the impact of gender ratio on secondary efficacy endpoints, the secondary endpoints will be analyzed as a sensitivity analysis by a mixed model for repeated measures (MMRM) where all post-baseline secondary endpoints (HbA1c levels, FBS levels, body weight, waist circumference, BMI, SBP and DBP) obtained at all planned visits before discontinuation from randomized treatment and visit and treatment are included as fixed factors and Baseline secondary endpoints and gender as covariates. Furthermore, interaction terms of visit by treatment, visit by gender and visit by respective Baseline secondary

endpoints will be included. An unstructured covariance matrix for respective Baseline secondary endpoint measurements within same patient will be employed. Regarding missing data this analysis approach relies on the assumption that data are missing at random. The estimated differences between each treatment groups at Week 52 and corresponding two sided p-values and 95% CI will be presented.

To evaluate the impact of gender ratio on secondary efficacy endpoint VAT/SAT area, VAT/SAT ratio and total body lean mass, these parameters will be analysed using ANCOVA model with treatment group as factor and Baseline test results and gender as a covariate on FAS and PPS population. The statistical modelling and analysis will be performed in the same manner as the primary efficacy variable using an ANCOVA model (Sensitivity Analysis).

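### An HbA1c taken at early exit can stand as the Week-52 result, so a subject who stopped study drug early can count as a glycaemic responder

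*SAP*

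**What the plan says.** SAP 3.8.2 defines the event: "the successful event is to achieve an HbA1c <7.0 at Week 52". For missing values it adds: "To obtain a complete data structure, missing data will be imputed using LOCF". SAP 3.1.4 sets no time limit ("Last observation will be carried forward as many times as needed") and takes a wide view of the source: "All available data, including unscheduled visits and rescue visits, will be taken into account when identifying the last observation to be carried forward". Protocol 8.4 has the same rule, confined to post-baseline values: "If no measurements is available at Week 52, the last post-baseline HbA1c prior to Week 52 will be used instead for analysis". For the mean change in HbA1c, SAP 3.8.2 uses a repeated-measures model with the opposite instruction: "Missing data will not be imputed".

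On early exit:

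- Protocol 3.9.1 requires the Visit 7 procedures, DXA included, within 7 days of stopping. Protocol 4.4 lists HbA1c among them.
- SAP 3.1.3 says these subjects are not followed further and that their early-termination data are shown with the end-of-treatment visit.
- Protocol 4.3 makes hypoglycaemia a reason for exit: "Subjects will discontinue the study if one major hypoglycaemic event or recurring minor hypoglycaemic events". Protocol 3.9 lists the same reason in permissive terms.

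Two checks are planned in SAP 3.8.3. In one, "the same model and statistics will be generated for FAS population with only truly observed data". The other repeats the secondary models in the per-protocol set, with the imputed responses retained.

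**The concern.** Neither document scores stopping study drug as non-response. An HbA1c measured at exit, on or within days of treatment, can therefore represent a time up to most of a year later when the subject is no longer on study drug. A subject withdrawn for a treatment harm may be recorded as a Week-52 success.

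This need not balance between arms. Protocol 1.1 describes hypoglycaemia as frequent with sulfonylureas, and Protocol 1.3 describes the risk with dapagliflozin as low by comparison. If low-HbA1c exits for hypoglycaemia occur, the protocol's own expectation puts most of them on glimepiride. The response odds ratio would then partly reflect the exit rule rather than control held to Week 52.

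**Working it through.** The plan states no response, exit or dropout rate for this endpoint, and the sample-size text is redacted, so there is no planned figure to reproduce. The check first traces who is affected and then sizes the effect under stated assumptions.

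**Who is affected.** SAP 2.1.4 admits a subject to the full analysis set only with a post-baseline total body fat value. Protocol section 4 schedules DXA at Visits 2 and 7 only. An early leaver therefore normally enters the set through the exit visit, which also supplies an HbA1c. There are then two possibilities.

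1. If the mapping in SAP 3.1.3 applies to the models as well as the tables, the exit HbA1c is the end-of-treatment value and LOCF is not needed.
2. If it does not, Week 52 is missing and LOCF brings the exit HbA1c forward.

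Both give the same score. An exit HbA1c of 7.0% or above is non-response either way, so only exits below 7.0% matter.

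**Inputs.** From the SAP: 120 subjects randomised 1:1, so 60 per arm. Assumed: every subject is in the full analysis set; durable response (below 7.0% at Week 52 on study drug) is 40% in both arms, or 24 of 60; there are k glimepiride exits with HbA1c below 7.0% and none on dapagliflozin.

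**Formulas.** One exit adds 1/60 = 1.67 points.

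- Exit value counted as Week 52: glimepiride rate = (24 + k)/60.
- Exits dropped: glimepiride rate = 24/(60 - k).
- Exits counted as non-response: 24/60 in both arms, OR = 1.00. This is the reference.
- OR is dapagliflozin vs glimepiride; the dapagliflozin odds are 24/36 = 0.667.

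| k | Rate, exit value used | Gap (points) | OR | Rate, exits dropped | OR |
|---|---|---|---|---|---|
| 1 | 25/60 = 41.7% | 1.7 | 0.93 | 24/59 = 40.7% | 0.97 |
| 3 | 27/60 = 45.0% | 5.0 | 0.81 | 24/57 = 42.1% | 0.92 |
| 6 | 30/60 = 50.0% | 10.0 | 0.67 | 24/54 = 44.4% | 0.83 |

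With durable response of 30% to 50%, the OR is 0.80-0.82 for three exits and 0.64-0.67 for six. With six glimepiride exits and one dapagliflozin exit at 40%, the gap is 8.3 points and the OR 0.71. On an unadjusted two-proportion approximation at 40%, the chance of a nominal p < 0.05 favouring glimepiride is about 8% with three exits and 19% with six, against 2.5% in that direction.

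**What the observed-data repeat recovers.** On the log scale, three exits give ln 0.815 = -0.205 with exit values used and ln 0.917 = -0.087 with exits dropped, so 1 - 0.087/0.205 = 58% of the shift is removed. For six exits, 1 - 0.182/0.405 = 55%. If exit values count as observed end-of-treatment values, nothing is removed. The per-protocol repeat keeps LOCF and does not test the rule.

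**The case against.** The strongest reply is that LOCF is not really the mechanism. A reader might infer from SAP 3.1.4 that values from the first post-baseline visit will routinely be carried to Week 52. The documents do not support that: a leaver without an exit DXA falls outside the full analysis set, and one with it should have an HbA1c from the same visit. Nor is the contrast with the repeated-measures model as sharp as it looks, because under the SAP 3.1.3 mapping the same exit value could enter that model at Week 52. This part of the objection stands. The point therefore concerns how exit values are used, with LOCF as one of two routes.

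A second reply is that the usual remedy, multiple imputation under missing at random, would not cure the problem. This also stands. Assume an arm mean of 7.2%, SD 0.8, exit HbA1c of 6.3-6.7% and correlation of 0.6-0.8 with Week 52. The conditional mean is 7.2 + r(exit - 7.2) and the SD is 0.8√(1 - r²). At 6.7% and r = 0.6 these are 6.90 and 0.64, a response probability of 56%. At 6.3% and r = 0.8 they are 6.48 and 0.48, or 86%. Such subjects remain mostly responders, because the method imputes as if treatment had continued.

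Third, exits may be few. Glimepiride can be down-titrated, Protocol 3.9 only permits discontinuation, and no passage says that subjects who exit for hypoglycaemia have HbA1c below 7.0%. Subjects discontinued for high HbA1c despite rescue score as non-responders in any case. This limits the size but leaves the rule unchanged.

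Finally, LOCF is the protocol's own method, the endpoint is secondary, and SAP 3.1.6 makes its test descriptive. That bears on priority, not on whether the rule is sound.

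**Conclusion.** The point holds in a limited form. As written, the SAP lets an HbA1c taken at early exit serve as the Week-52 result, so stopping study drug with HbA1c below 7.0% and an exit DXA is scored as response. The size is conditional: about 1.7 points per such exit in a 60-subject arm, and an OR of 0.81-0.67 for three to six glimepiride exits under the assumed 40% durable response and no dapagliflozin exits. With one or two exits the effect is small.

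Three stronger readings should be resisted.

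- The documents do not show that the odds ratio will be biased by a given amount. The rates are assumed, and the shift is measured against scoring early stoppers as non-responders. Against response had treatment continued, the exit value could be right or wrong.
- They do not show a rule tilted towards the sponsor's drug. On the protocol's expectation it works the other way.
- They do not leave the endpoint without checks. The observed-data repeat removes over half of the log-odds shift if exit values are excluded from it, but the SAP does not say whether they are.

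The primary conclusion is untouched. The SAP's missing post-baseline limit hardly matters, since a qualifying screening HbA1c of at least 7.0% carried forward gives non-response.

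**What to change.** 1. In SAP 3.1.3 and 3.1.4, state that an early-termination HbA1c outside the Week-52 ±7-day window is not a Week-52 value, either for the responder analysis or for the observed-data repeat.
2. In SAP 3.8.2 and 3.8.3, add an analysis that counts subjects who stopped study drug before Week 52 as non-responders, and report it beside the LOCF result.
3. Optionally, add multiple imputation from the HbA1c repeated-measures model, dichotomised at 7.0%. Label it as estimating response had treatment continued, since it does not by itself correct for stopping.
4. Keep LOCF for continuity with the protocol, and record the changes in SAP section 4, which now lists none. If the database is already locked, add the new analyses as labelled supportive ones.

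The cost is SAP wording and a little programming, with no new data. The added responder rate may be slightly lower than under LOCF.

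Separately, Protocol 3.9 (permissive, discontinuation of investigational product) and Protocol 4.3 (mandatory, discontinuation of the study) differ on hypoglycaemia. They must be reconciled, because they determine how many such exits occur.

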### **3.8.3 Sensitivity Analysis of Secondary Endpoints**

To assess the robustness of the missing data imputation (LOCF), the same model and statistics will be generated for FAS population with only truly observed data when evaluating proportion of subjects achieving a glycemic response.

To evaluate the impact of protocol compliance on secondary efficacy endpoint, secondary efficacy models (with imputed data for glycemic response) method will be repeated on the PPS population.

To evaluate the impact of gender ratio on secondary efficacy endpoints, the secondary endpoints will be analyzed as a sensitivity analysis by a mixed model for repeated measures (MMRM) where all post-baseline secondary endpoints (HbA1c levels, FBS levels, body weight, waist circumference, BMI, SBP and DBP) obtained at all planned visits before discontinuation from randomized treatment and visit and treatment are included as fixed factors and Baseline secondary endpoints and gender as covariates. Furthermore, interaction terms of visit by treatment, visit by gender and visit by respective Baseline secondary

endpoints will be included. An unstructured covariance matrix for respective Baseline secondary endpoint measurements within same patient will be employed. Regarding missing data this analysis approach relies on the assumption that data are missing at random. The estimated differences between each treatment groups at Week 52 and corresponding two sided p-values and 95% CI will be presented.

To evaluate the impact of gender ratio on secondary efficacy endpoint VAT/SAT area, VAT/SAT ratio and total body lean mass, these parameters will be analysed using ANCOVA model with treatment group as factor and Baseline test results and gender as a covariate on FAS and PPS population. The statistical modelling and analysis will be performed in the same manner as the primary efficacy variable using an ANCOVA model (Sensitivity Analysis).

